### Phase III-IV liver chemistry increased monitoring criteria with continued therapy

Liver Chemistry Increased Monitoring Criteria – Liver Monitoring Event	
Criteria	Actions
ALT $\geq$ 5xULN and $<$ 8xULN and bilirubin $<$ 2xULN without symptoms believed to be related to liver injury or hypersensitivity, and who can be monitored weekly for 2 weeks. OR ALT $\geq$ 3xULN and $<$ 5xULN and bilirubin	
 
Notify the GSK medical monitor within 24 hours of learning of the abnormality to discuss subject safety.
 
Subject can continue study treatment
 
Subject must return weekly for repeat liver chemistries (ALT, AST, alkaline phosphatase,
 

<2xULN without symptoms believed to be related to liver injury or hypersensitivity, and who can be monitored weekly for 4 weeks.
	
bilirubin) until they resolve, stabilise or return to within baseline
 

• If at any time subject meets the liver chemistry stopping criteria, proceed as described above

• If ALT decreases from ALT <math>\geq</math>5xULN and <8xULN to <math>\geq</math>3xULN but <5xULN, continue to monitor liver chemistries weekly.

• If, after 4 weeks of monitoring, ALT <3xULN and bilirubin <2xULN, monitor subjects twice monthly until liver chemistries normalize or return to within baseline.

--	--

## 12.6. Appendix 6: Definition of and Procedures for Recording, Evaluating, Follow-up and Reporting of Adverse Events

### 12.6.1. Definition of Adverse Events

#### Adverse Event Definition:

- An AE is any untoward medical occurrence in a patient or clinical investigation subject, temporally associated with the use of a medicinal product, whether or not considered related to the medicinal product.
- NOTE: An AE can therefore be any unfavorable and unintended sign (including an abnormal laboratory finding), symptom, or disease (new or exacerbated) temporally associated with the use of a medicinal product.

#### Events meeting AE definition include:

- Any abnormal laboratory test results (hematology, clinical chemistry, or urinalysis) or other safety assessments (e.g., ECGs, radiological scans, vital signs measurements), including those that worsen from baseline, and felt to be clinically significant in the medical and scientific judgement of the investigator.
- Exacerbation of a chronic or intermittent pre-existing condition including either an increase in frequency and/or intensity of the condition.
- New conditions detected or diagnosed after study treatment administration even though it may have been present prior to the start of the study.
- Signs, symptoms, or the clinical sequelae of a suspected interaction.
- Signs, symptoms, or the clinical sequelae of a suspected overdose of either study treatment or a concomitant medication (overdose per se will not be reported as an AE/SAE unless this is an intentional overdose taken with possible suicidal/self-harming intent. This should be reported regardless of sequelae).
- "Lack of efficacy" or "failure of expected pharmacological action" per se will not be reported as an AE or SAE. However, the signs and symptoms and/or clinical sequelae resulting from lack of efficacy will be reported if they fulfil the definition of an AE or SAE.

#### Events NOT meeting definition of an AE include:

- Any clinically significant abnormal laboratory findings or other abnormal safety assessments which are associated with the underlying disease, unless judged by the investigator to be more severe than expected for the subject's condition.
- The disease/disorder being studied or expected progression, signs, or symptoms of the disease/disorder being studied, unless more severe than expected for the subject's condition.
- Medical or surgical procedure (e.g., endoscopy, appendectomy): the condition that leads to the procedure is an AE.
- Situations where an untoward medical occurrence did not occur (social and/or convenience admission to a hospital).
- Anticipated day-to-day fluctuations of pre-existing disease(s) or condition(s) present or detected at the start of the study that do not worsen.

### 12.6.2. Definition of Serious Adverse Events

If an event is not an AE per definition above, then it cannot be an SAE even if serious conditions are met (e.g., hospitalization for signs/symptoms of the disease under study, death due to progression of disease, etc).

Serious Adverse Event (SAE) is defined as any untoward medical occurrence that, at any dose:	
a. Results in death	
b. Is life-threatening	
NOTE:	
	The term 'life-threatening' in the definition of 'serious' refers to an event in which the subject was at risk of death at the time of the event. It does not refer to an event, which hypothetically might have caused death, if it were more severe.
c. Requires hospitalization or prolongation of existing hospitalization	
NOTE:	
	
 
• In general, hospitalization signifies that the subject has been detained (usually involving at least an overnight stay) at the hospital or emergency ward for observation and/or treatment that would not have been appropriate in the physician's office or out-patient setting. Complications that occur during hospitalization are AEs. If a complication prolongs hospitalization or fulfills any other serious criteria, the event is serious. When in doubt as to whether "hospitalization" occurred or was necessary, the AE should be considered serious.
 
• Hospitalization for elective treatment of a pre-existing condition that did not worsen from baseline is not considered an AE.
 

d. Results in disability/incapacity	
NOTE:	
	
 
• The term disability means a substantial disruption of a person's ability to conduct normal life functions.
 
• This definition is not intended to include experiences of relatively minor medical significance such as uncomplicated headache, nausea, vomiting, diarrhea, influenza, and accidental trauma (e.g. sprained ankle) which may interfere or prevent everyday life functions but do not constitute a substantial disruption
 

e. Is a congenital anomaly/birth defect	
f. Other situations:	
	
 
• Medical or scientific judgment should be exercised in deciding whether reporting is appropriate in other situations, such as important medical events that may not be immediately life-threatening or result in death or hospitalization but may jeopardize the subject or may require medical or surgical intervention to prevent one of the other outcomes listed in the above definition. These should also be considered serious.
 
• Examples of such events are invasive or malignant cancers, intensive treatment in an emergency room or at home for allergic bronchospasm, blood dyscrasias or convulsions that do not result in hospitalization, or development of drug dependency or drug abuse
 

g. Is associated with liver injury and impaired liver function defined as:	
	
 
• ALT <math>\geq</math> 3xULN and total bilirubin* <math>\geq</math> 2xULN (>35% direct), or
 
• ALT <math>\geq</math> 3xULN and INR** <math>></math> 1.5.
 

\* Serum bilirubin fractionation should be performed if testing is available; (for ND patients only) if

unavailable, record presence of detectable urinary bilirubin on dipstick, indicating direct bilirubin elevations and suggesting liver injury. If fractionation is unavailable and ALT  $\geq$  3xULN and total bilirubin  $\geq$  2xULN, then the event is still to be reported as an SAE.

\*\* INR testing not required per protocol and the threshold value does not apply to subjects receiving anticoagulants. If INR measurement is obtained, the value is to be recorded on the SAE form.

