**7.4.1.1. Time period and Frequency for collecting AE and SAE information**

- AEs and SAEs will be collected from the start of Study Treatment until the follow-up contact (see Section 7.4.1.3.), at the timepoints specified in the Time and Events Table (Table 14).
- Medical occurrences that begin prior to the start of study treatment but after obtaining informed consent may be recorded on the Medical History/Current Medical Conditions section of the CRF.
- Any SAEs assessed as related to study participation (e.g., protocol-mandated procedures, invasive tests, or change in existing therapy) or related to a GSK product will be recorded from the time a subject consents to participate in the study up to and including any follow-up contact.
- All SAEs will be recorded and reported to GSK within 24 hours, as indicated in Section 12.6. Appendix 6.
- Investigators are not obligated to actively seek AEs or SAEs in former study subjects. However, if the investigator learns of any SAE, including a death, at any time after a subject has been discharged from the study, and he/she considers the event reasonably related to the study treatment or study participation, the investigator must promptly notify GSK.

NOTE: The method of recording, evaluating and assessing causality of AEs and SAEs plus procedures for completing and transmitting SAE reports to GSK are provided in Section 12.6. Appendix 6.

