#### **7.4.2. Adverse Events of Special Interest**

The investigator (or subinvestigator) or designee will be responsible for detecting, documenting, and reporting any AEs of special interest listed below. These events have been identified based on the known safety profiles of ESAs, theoretical or potential risks based on the mechanism of action of GSK1278863, and findings from completed nonclinical studies of GSK1278863.

- Thrombosis and/or tissue ischemia secondary to excessive erythropoiesis
- Death, myocardial infarction, stroke, heart failure, thromboembolic events, thrombosis of vascular access
- Cardiomyopathy
- Pulmonary artery hypertension
- Cancer-related mortality and tumor progression and recurrence
- Esophageal and gastric erosions
- Proliferative retinopathy, macular edema, choroidal neovascularization
- Exacerbation of rheumatoid arthritis

Any relevant AE should be recorded in the relevant section of the subject's eCRF.

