## 12.2. Appendix 2: Risk Assessment

Potential Risk of Clinical Significance	Summary of Data/Rationale for Risk	Mitigation Strategy
GSK1278863		
Excessive erythropoiesis (polycythemia) leading to thrombosis and/or tissue ischemia	
In animal studies, excessive erythropoiesis attributed to GSK1278863 was associated with vascular congestion, microthrombi, and tissue ischemia in a number of organs.
 
Following review of clinical data received to date, this has not been identified as a safety concern for GSK1278863.
 
Phase 2 dose-ranging studies, and associated statistical and exposure response modelling has informed Phase 3 dose rationale, starting doses, dose levels, and dose adjustment scheme to optimize Hgb management.
	
 
Specific eligibility criteria related to requirements for entry Hgb are detailed in Section 5.1.
 
Hgb will be closely monitored throughout the dosing period as outlined in the Time and Events Table Section 7.1.
 
Specific guidance for dose adjustment, dose interruption, or discontinuation of GSK1278863 based on achieved Hgb is provided in Section 6.4.1.
 
These risks have been identified as AEs of special interest and will be monitored instreamly by the internal safety review team throughout the study period.
 

Risk of death, MI, stroke, heart failure, thromboembolic events, thrombosis of vascular access at Hgb levels which are within the normal range (i.e. not polycythemic conditions)	
Marketed rhEPO/ESAs have been associated with an increased risk for death and serious cardiovascular events when used in patients with anemia of CKD.
 
Following review of clinical data received to date, this has not been identified as a safety concern for GSK1278863.
	
 
Specific eligibility criteria related to CV risk are outlined in Section 5.2.
 
Hgb will be closely monitored throughout the dosing period as outlined in the Time and Events Table Section 7.1.
 
These risks have been identified as AEs of special interest and will be monitored instreamly by the internal safety review team throughout the study period.
 

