#### Assessment of Causality

- The investigator is obligated to assess the relationship between study treatment and the occurrence of each AE/SAE.
- A "reasonable possibility" is meant to convey that there are facts/evidence or arguments to suggest a causal relationship, rather than a relationship cannot be ruled out.
- The investigator will use clinical judgment to determine the relationship.
- Alternative causes, such as natural history of the underlying diseases, concomitant therapy, other risk factors, and the temporal relationship of the event to the study treatment will be considered and investigated.
- The investigator will also consult the Investigator Brochure (IB) and/or Product Information, for marketed products, in the determination of his/her assessment.
- For each AE/SAE the investigator must document in the medical notes that he/she has reviewed the AE/SAE and has provided an assessment of causality.
- There may be situations when an SAE has occurred and the investigator has minimal information to include in the initial report to GSK. However, **it is very important that the investigator always make an assessment of causality for every event prior to the initial transmission of the SAE data to GSK.**
- The investigator may change his/her opinion of causality in light of follow-up information, amending the SAE data collection tool accordingly.
- The causality assessment is one of the criteria used when determining regulatory reporting requirements.

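### An unblinded judgement of expected disease progression can take a death outside AE and SAE status; a short carve-out for deaths in Appendix 6 would close the gap (minor)

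*Protocol*

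**What the plan says.** The general rule in Section 12.6.2 is: "If an event is not an AE per definition above, then it cannot be an SAE even if serious conditions are met". The clause that closes it carries two examples, a hospitalization for the disease under study and a death from its progression: "even if serious conditions are met (e.g., hospitalization for signs/symptoms of the disease under study, death due to progression of disease, etc".

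The AE definition behind that rule is in Section 12.6.1. Among events that are not AEs it lists "expected progression, signs, or symptoms of the disease/disorder being studied, unless more severe than expected" for the subject's condition. Among events that are AEs it lists "Exacerbation of a chronic or intermittent pre-existing condition including either an increase in frequency and/or intensity of the condition".

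Section 7.4.2 makes the investigator responsible for detecting, documenting and reporting AEs of special interest. One entry on its list reads "Death, myocardial infarction, stroke, heart failure, thromboembolic events, thrombosis of vascular access", with no limit on the cause of death. The corresponding row of Appendix 2 (Section 12.2) reads "Risk of death, MI, stroke, heart failure, thromboembolic events, thrombosis of vascular access at Hgb levels which are within the normal range". It is limited by Hgb level but not by cause.

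Three duties follow from AE or SAE status:
- Section 7.4.1.1: "All SAEs will be recorded and reported to GSK within 24 hours".
- Section 12.6.5: "The investigator is obligated to assess the relationship between study treatment and the occurrence of each AE/SAE".
- Section 9.4.4.2: AEs, SAEs and AEs of special interest are each tabulated.

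Two duties do not depend on it. Section 7.4.1.4 requires the Death section of the CRF for all deaths, whether or not they count as SAEs. Section 12.6.5 requires a copy of any post-mortem findings.

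**The concern.** The trial is open-label (Section 6.5), so the investigator who decides whether a death is expected progression knows the treatment. For such a death, that decision settles whether the sponsor hears of it as an SAE within 24 hours, whether relatedness to treatment must be assessed, and whether it appears in the safety tables.

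Death is not an incidental outcome here. Appendix 2 records that marketed ESAs have been associated with increased risk of death in patients with anemia of CKD. It also commits the sponsor's internal safety team to monitor the listed events while the study runs. A death that drops out of AE status on attribution alone could miss the route that this monitoring relies on.

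The wording governs what sites do during the trial, so a later choice of analysis cannot fully repair it.

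**Working it through.** No arithmetic applies. The check sets the sections side by side and follows one death through them.

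**Step 1. Can a death fail to be an AE?** Yes, narrowly. Section 12.6.1 excludes expected progression of the disease under study. It keeps as AEs whatever is more severe than expected for that subject, and it keeps exacerbations of pre-existing conditions. Only a death judged to be expected progression falls out.

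**Step 2. Can that death still be an SAE?** No. Section 12.6.2 makes AE status a precondition and uses this kind of death as an example. Section 7.4.1.4 confirms that the protocol treats non-SAE deaths as possible, since it asks for the Death CRF whether or not the death is an SAE.

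**Step 3. Is that death an AE of special interest?** The protocol does not say. If Section 7.4.2 is a subset of AEs, the death is excluded. If its entry for death is taken at face value, the death is included.

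**Step 4. What turns on the classification?**

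| Item | Section | Depends on AE status? |
|---|---|---|
| 24-hour SAE report | 7.4.1.1 | Yes |
| Causality assessment | 12.6.5 | Yes |
| AE and SAE summaries | 9.4.4.2 | Yes |
| Special-interest summary | 7.4.2, 9.4.4.2 | Yes if 7.4.2 is a subset of AEs; otherwise unclear |
| Death CRF | 7.4.1.4 | No |
| Post-mortem findings | 12.6.5 | No |

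The dependent items are consequences of one decision, not separate defects.

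**Step 5. Does the Death CRF replace what is lost?** In part. It is completed for every death, so deaths can be counted by arm. It is due within one week of the report of death, against 24 hours for an SAE. The content that Section 7.4.1.4 describes distinguishes cardiovascular from non-cardiovascular death; the section mentions no assessment of relationship to study treatment.

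**Step 6. How many deaths?** The protocol gives no figure from which to estimate this. Section 6.10 calls the target disease not life-threatening. If the disease under study is renal anemia, almost no death would qualify. If a site reads it as the underlying CKD (stages 3 to 5 are enrolled, Section 5.1), more could. Either way, the limits in Step 1 keep the number small.

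**The case against.** The strongest reply is that the sections agree once they are read in order. Section 7.4.1 places the AE and SAE definitions in Appendix 6. Section 7.4.2 concerns AEs of special interest and closes by asking that relevant AEs be recorded, so it selects from AEs and does not redefine them. AE status comes first, then seriousness, then special interest. The protocol also foresees deaths that are not SAEs and gives them their own form. AE status rests on investigator judgement for many events, so nothing here is peculiar to death.

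Most of this stands. A reader might infer that Sections 12.6.2 and 7.4.2 contradict each other; the subset reading is available, so the text does not support that. A reader might infer that deaths go missing or that the mortality comparison between arms is biased; Section 7.4.1.4 captures every death, and nothing in the protocol indicates a direction of bias. A reader might also take Section 12.6.2 to exclude deaths in general; its rule is conditional and reaches only events that are not AEs. The Appendix 2 row is a risk description limited to normal Hgb levels, not a reporting rule.

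What the reply does not remove is the practical consequence. Even on the subset reading, an unblinded attribution decides whether such a death is reported within 24 hours, assessed for causality and tabulated.

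**Conclusion.** The point holds as a minor, cheap improvement to safety reporting. Sections 12.6.1 and 12.6.2 let a death attributed to expected progression be neither an AE nor an SAE, although the protocol names death both as an AE of special interest and as a risk. The harm is confined to expedited reporting, causality assessment and entry in the AE, SAE and special-interest summaries for what are probably very few deaths. All-cause mortality by arm can still be compared, and the primary Hgb analysis is untouched.

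This rests on two assumptions: that sites apply Appendix 6 as written, and that no instruction outside the protocol already requires every death to be reported as an SAE.

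**What to change.** In Section 12.6.2, delete the example of death from disease progression (the hospitalization example can stay) and add:

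> *Notwithstanding Section 12.6.1 and the rule above, every death on study, whatever its attributed cause, is recorded as an AE, reported as an SAE within 24 hours with a causality assessment, and counted as an AE of special interest (Section 7.4.2).*

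Add a matching exception for deaths to the expected-progression bullet in Section 12.6.1. Both parts are needed. A bare statement that every death is an SAE would collide with the general rule left in Section 12.6.2 and with the exclusion in Section 12.6.1.

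Stating instead that Section 7.4.2 leaves out deaths from expected progression would settle the wording, but the reporting of those deaths would still depend on the unblinded attribution.

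The cost is a deletion, one sentence, one exception and a note to sites. The Death CRF is already completed for every death. The only downside is possibly a few more expedited reports.

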### 12.6.3. Definition of Cardiovascular Events

#### Cardiovascular Events (CV) Definition:

Investigators will be required to fill out the specific CV event page of the CRF for the following AEs and SAEs:

- Myocardial infarction/unstable angina
- Congestive heart failure
- Arrhythmias
- Valvulopathy
- Pulmonary hypertension
- Cerebrovascular events/stroke and transient ischemic attack
- Peripheral arterial thromboembolism
- Deep venous thrombosis/pulmonary embolism
- Revascularization

### 12.6.4. Recording of AEs and SAEs

#### AEs and SAE Recording:

- When an AE/SAE occurs, it is the responsibility of the investigator to review all documentation (e.g., hospital progress notes, laboratory, and diagnostics reports) relative to the event.
- The investigator will then record all relevant information regarding an AE/SAE in the CRF
- It is not acceptable for the investigator to send photocopies of the subject's medical records to GSK in lieu of completion of the GSK, AE/SAE CRF page.
- There may be instances when copies of medical records for certain cases are requested by GSK. In this instance, all subject identifiers, with the exception of the subject number, will be blinded on the copies of the medical records prior to submission of to GSK.
- The investigator will attempt to establish a diagnosis of the event based on signs, symptoms, and/or other clinical information. In such cases, the diagnosis will be documented as the AE/SAE and not the individual signs/symptoms.
- PRO questionnaires and the collection of AE data are independent components of the study.
- Responses to each question in PRO questionnaire will be treated in accordance with standard scoring and statistical procedures detailed by the scale's developer.
- The use of a single question from a multidimensional health survey to designate a cause-effect relationship to an AE is inappropriate.

### 12.6.5. Evaluating AEs and SAEs

#### Assessment of Intensity

The investigator will make an assessment of intensity for each AE and SAE reported during the study and will assign it to one of the following categories:

- Mild: An event that is easily tolerated by the subject, causing minimal discomfort and not interfering with everyday activities.
- Moderate: An event that is sufficiently discomforting to interfere with normal everyday activities
- Severe: An event that prevents normal everyday activities. - an AE that is assessed as severe will not be confused with an SAE. Severity is a category utilized for rating the intensity of an event; and both AEs and SAEs can be assessed as severe.
- An event is defined as 'serious' when it meets at least one of the pre-defined outcomes as described in the definition of an SAE.

